## **Outcome Measures**

### **Primary Outcome Measures:**

1. Number of examined participants with diabetes per retina specialist working hour
  - a. Number of examined participants with diabetes per retina specialist working hour. Numerator is the number of examined participants (including persons evaluated by autonomous AI on Intervention Days who are determined not to need to see the retina specialist). The denominator is retina specialist working time in hours.
2. Number of (all) patients per retina specialist working hour
  - a. Number of examined patients (all types) per retina specialist working hour. Numerator is the number of examined participants (including persons evaluated by autonomous AI on Intervention Days who are determined not to need to see the retina specialist). The denominator is retina specialist working time in hours.

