### 2. Outcome Measures

#### 2.1. Main Study Outcome:

The number of examined patients with diabetes per retina specialist working hour between AI and non-AI days.

- Numerator: number of examined patients
  - Sum of the number of patients diagnosed with diabetes mellitus (type 1 or type 2) examined for DR per day
  - Patients included have not been previously diagnosed with DR
  - Includes all patients evaluated by autonomous AI on AI days, even if they are not seen by the retina specialist
- Denominator: retina specialist working time (hours)
  - Sum of retina specialist time spent on all diabetes patients examined per day
  - Does not include patient time spent during autonomous AI evaluation
  - Excluding treatment or surgical time
  - Including retina specialist time spent on ordering & reviewing diagnostic studies and scheduling treatment/surgery

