### 3.2. Data Completion

- Questionnaires will be completed by specialist participants at the end of the trial.
- AI-eligible patient demographic data will be completed prior to the AI exam, and applicable satisfaction surveys will be completed following the AI exam.
- Specialist hours will be tracked daily for clinic time and number of clinic exams completed by each specialist will be tracked daily (all patients examined and patients with diabetes examined)

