## 4. Sample Size Calculations

The null hypothesis is that diabetic patients without known DR seen by retina specialist per doctor hour for regular clinic days and AI days are the same. We are estimating the sample size needed to reject this null hypothesis. In calculating the sample size we used 80% power (the probability of rejecting a false null hypothesis). The sample size estimate is 924 patient participants.

Inputs for the sample size estimate calculations are:

- 80% power; power is the probability of rejecting a false null hypothesis.
- Alpha of 5%; probability of rejecting a true null hypothesis.
- Average cluster size of 8 and cluster size coefficient of variation of 0.45 (based on March data).
- Mean number of diabetic patients without known DR seen per doctor hour is 1.34 (based on Quarter 1 data). Hospital records that were used to calculate the sample size show that there are approximately 366 diabetic patients seen at the hospital per month. The retina clinic examines approximately 237 patients with diabetes per month.
- We changed some factors, but decided on one estimate.

Mean of Group 1	Mean of Group 2	Mean Difference	Intra-cluster correlation coefficient	Sample Size estimate
-----------------	-----------------	-----------------	---------------------------------------	----------------------

1.34	1.68	0.34	0.15	924
------	------	------	------	-----

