## 6. Analysis

Raw and adjusted (for above physician and patient predictors of productivity) group differences in the number of patients with diabetic retinopathy passing through the clinic per hour per physician will be calculated for AI and non-AI days. The two clinic day patient groups will be compared with Chi-square testing for categorical variables. Age as a continuous variable was summarized with mean and standard deviation and the two groups will be compared with the student t-test.

Study outcomes of encounters per retina specialist hour and confidence intervals will be calculated for each clinic day for all patients, as well as specifically for diabetic patients and retina specialty patients. Rates will be compared across AI and non-AI clinic days with student t-testing. Associations between the main outcome, diabetic patients examined per hour, and potential predictors will be assessed utilizing linear regression modeling with generalized estimating equations that include clustering effect of day. Residuals will be assessed to confirm that a linear model fits the rate outcome. A multivariable model will include sex, gender and variables that have  $p\text{-value} < 0.10$  in the univariate analysis.

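### SAP 6 pools one variance for AI and control days although the SAP 2.1 rate is likely to vary more on AI days; Welch's test is a free improvement when day counts differ

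*Combined protocol and SAP*

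**What the plan says.** SAP 6 (Analysis) sets the unadjusted comparison: "Rates will be compared across AI and non-AI clinic days with student t-testing". It names no unequal-variance or skew-robust method for that comparison. It also plans a linear GEE model for predictors of the main outcome, with this check: "Residuals will be assessed to confirm that a linear model fits the rate outcome". No consequence is stated if the check fails.

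SAP 2.1 defines the rate. The numerator is limited to diabetes patients without an earlier DR diagnosis and has this rule: "Includes all patients evaluated by autonomous AI on AI days, even if they are not seen by the retina specialist". The denominator is "Sum of retina specialist time spent on all diabetes patients examined per day", and for AI time: "Does not include patient time spent during autonomous AI evaluation".

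Two other places describe the hours differently. The protocol's Primary Outcome Measures say "The denominator is retina specialist working time in hours", and SAP 3.2 says "Specialist hours will be tracked daily for clinic time".

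The protocol and SAP 5 randomise clinic days but give neither an allocation ratio nor a rule that balances the number of days.

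**The concern.** On a control day, patients and specialist time rise and fall together, so the daily rate is fairly stable. On an AI day each cleared patient adds one to the count and nothing to the time. If no other diabetes patients were in the denominator, the rate would be scaled by about 1/(1 - share cleared that day). With about 8 patients a day that share moves a good deal between days, which widens the spread of AI-day rates and gives them a right tail.

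Pooling the variances does little harm when the day counts are equal. When AI days are fewer, the pooled standard error is too small; when they are more numerous, it is too large. At stake is the interval around the gain in productivity, which is the trial's main result.

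**Working it through.** **Inputs from the documents.** SAP 4: mean day size 8, CV 0.45, control rate 1.34, AI rate 1.68, difference 0.34, ICC 0.15, 924 patients; for alpha, "Alpha of 5%; probability of rejecting a true null hypothesis" (taken as two-sided).

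**The plan's own figure.** The documents state no coverage, SD or variance ratio; the nearest figure is 924. Design effect: 1 + ((1 + 0.45²) × 8 - 1) × 0.15 = 2.293. The SD is not given. With a Poisson-type variance of (1.34 + 1.68)/2 = 1.51, the size per arm is 2 × 1.51 × (1.960 + 0.842)²/0.34² = 205.05, rounded up to 206. The total is 206 × 2 × 2.293 = 945, within 3% of 924. So 924 is compatible with the inputs but is not uniquely reproduced. It implies 924/8 = 115.5, or about 116 clinic days.

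**Assumptions not in the documents.** Share cleared 20%, which the planned gain would imply if nobody else were in the denominator (1 - 1.34/1.68 = 0.202); per-patient time CV 0.5; day-to-day speed SD 0.2-0.4 on the log scale; 0 to 3 always-seen diabetes patients a day; AI days with zero time left out.

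**Step 1: variance ratio R (AI/control).** Simulated clinic days give R of about 3.5-5.4 with no always-seen patients and 2.0-2.5 with 3 a day.

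**Step 2: what pooling does.** For large samples,

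- Student's squared standard error ≈ σ²(control)/n(AI) + σ²(AI)/n(control)
- the correct one = σ²(control)/n(control) + σ²(AI)/n(AI)

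The two day counts are swapped. At 58/58 the expressions are identical whatever R is. At 68 control/48 AI days:

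- R = 5.4: (1/48 + 5.4/68)/(1/68 + 5.4/48) = 0.1002/0.1272 = 0.788. The standard error is √0.788 = 0.888 of what it should be, and coverage is 2Φ(1.96 × 0.888) - 1 = 91.8%.
- R = 2: (1/48 + 2/68)/(1/68 + 2/48) = 0.0502/0.0564 = 0.891; √0.891 = 0.944; coverage 93.6%.

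**Step 3: simulated coverage with the skew included.**

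| Days (control/AI) | Always-seen patients | Student coverage |
|---|---|---|
| 58/58 | 0 | about 94% |
| 58/58 | 3 a day | about 95% |
| 68/48 | 0 | 91-92% |
| 68/48 | 3 a day | 93-94% |
| 48/68 | 0 | about 96% |

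Welch recovers about 1-2 points at 68/48 (for example 91.3% to 93.3%). At 58/58 it changes coverage by less than 0.3 points, so the small loss there is due to skew.

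**Step 4: how likely is a harmful split?** Under simple randomisation, AI days ~ Binomial(116, 0.5). P(48 or fewer) = 3.9%; P(53 or fewer) = 20%. Only this tail causes under-coverage.

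**Step 5: fixed clinic hours as denominator.** R = (1.68/1.34)² = 1.57. At 68/48: (1/48 + 1.57/68)/(1/68 + 1.57/48) = 0.926; √0.926 = 0.962; coverage 94.1%, a loss of about 1 point. At 58/58 it is 95%.

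**Harsher case.** A second clinic-day model (day-effect CV 0.15, at least 2 patients a day, 0-4 other diabetes patients a day) also let clearing cluster by day (ICC 0 to 0.15). At 58/58 and a 1.25-fold gain, coverage was 88.6-94.6% for Student, 88.8-94.7% for Welch and 94.2-95.6% for a ratio of totals on the log scale, which is a different estimand. Nothing in the documents fixes that clustering.

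**The case against.** A reader might infer that the planned interval definitely lacks 95% coverage, that unequal variance is the cause, or that the test gives too many false positives. The documents do not support any of these.

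- **Level.** If AI removes no specialist time, both kinds of day share one distribution and the 5% level holds. This stands.
- **Equal day counts.** Student and Welch then have the same standard error. Coverage at the planned gain is about 94-95% under the main assumptions, and any loss is skew. This stands.
- **Denominator.** SAP 2.1 counts time on all diabetes patients, whereas its numerator leaves out those already diagnosed with DR. Patients not eligible for AI always see the specialist, so their time damps the instability. Zero such patients is the worst case. This stands and is why a range is given.
- **Clinic time.** Under the wording of the protocol's outcome section and SAP 3.2, the effect largely disappears. SAP 2.1 is the SAP's explicit definition, however, so the point is reduced and not removed.
- **Interval and GEE.** SAP 6 mentions intervals for each clinic day and defines none for the AI-minus-control difference; the interval discussed here is the one a t-test would ordinarily supply. GEE inference customarily uses a robust variance that does not pool across arms, but the SAP does not say so and still names Student for the rate comparison.

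It is also tempting to make log rates the main analysis. That changes the estimand: the plan is sized on a difference of 0.34. In the 20% model without always-seen patients the ratio of arithmetic means is 1.34 and of geometric means 1.28, and neither equals 1.68/1.34 = 1.25. Log rates also leave zero-time days undefined.

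**Conclusion.** The point holds in a limited form. By the SAP 2.1 definition, AI-day rates are likely to be more variable and more skewed, and SAP 6 pools the variances without fixing equal day counts. The interval may therefore fall short of 95%. Under the main assumptions the shortfall is at most about 1 point at equal counts and about 1 to 4 points at 68/48, a split at least that short of AI days having a probability of about 4%. With more AI than control days, the interval is slightly too wide instead.

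These sizes rest on the share cleared, the day-to-day spread and the number of always-seen patients, none of which is in the documents. Day-clustered clearing would make the loss larger, and fixed clinic time would nearly remove it. This is an inexpensive improvement and does not show that the planned analysis is invalid.

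**What to change.** 1. In SAP 6, name Welch's unequal-variance t-test in place of Student's for the daily rates, and report the difference in mean daily rate (AI minus control) with its 95% confidence interval. This keeps the planned estimand, costs nothing at equal day counts, and needs no extra data or patients.
2. Welch does not repair skew. Add one prespecified sensitivity analysis that is robust to it, such as log daily rates or a ratio of totals with day-level resampling, and label it as a different estimand.
3. State how AI days with zero specialist time are handled. They were 0.4-1.5% of AI days in the main model without always-seen patients (20-40% cleared), and up to about 6% in the most extreme case tried.
4. Reconcile the denominator wording in the protocol's Primary Outcome Measures, SAP 2.1 and SAP 3.2, since the size of this problem depends on which one is meant.

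The cost is a few SAP sentences and one additional analysis.

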## 5. Randomization and Masking

The Bangladesh **PRODUCTIV**ity in **Eyecare** (B-PRODUCTIVE) Trial is a cluster-randomized (by clinic day) controlled trial. The study will assess the change in number of examined patients with diabetes per retina specialist working hour for three fully-qualified ophthalmologists regularly seeing patients with DR. All eligible patients (aged  $\geq 22$ , known diabetes, no previous DR diagnosis, consented) receive autonomous AI for DR detection. This is done for purposes of masking (neither patients nor physicians know the group assignment of eligible patients) and concealment. On randomly selected “Intervention” clinic days, if eligible patients receive a positive DR diagnosis or have insufficient image quality, they continue to the ophthalmologist. If eligible patients receive a negative DR diagnosis, they do not see the retina specialist, and are referred for a visit at the regular eye clinic (not the retina clinic) in 3 months. On randomly selected “Control Days,” all patients see the ophthalmologist, irrespective of the results of the autonomous AI report. The retina doctors are masked both to patient group assignment (that is, whether autonomous AI was used or not on the particular clinic day) and also masked to the results of the autonomous AI on Intervention days. Patients are also masked to group assignment and autonomous AI results.

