## 6.2 Baseline characteristics

Clinic characteristics include number of clinic hours per day, total clinic hours during the trial, total completed specialist visits for diabetes patients and total completed specialist visits for all patients.

AI-eligible patient characteristics include age, sex, and estimated monthly income.

Specialist participant characteristics include age, sex, and years as a retina specialist.

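### SAP 6 would test physician predictors with clustering on day only; if specialist age, sex and experience are meant, three specialists cannot support those tests

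*Combined protocol and SAP*

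**What the plan says.** SAP 6 (Analysis) plans "Raw and adjusted (for above physician and patient predictors of productivity) group differences" between AI and non-AI days. The protocol's outline of the main analysis plans the same adjustment. In neither place does a list of predictors precede the word 'above'.

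SAP 6 then says that for the main outcome "potential predictors will be assessed utilizing linear regression modeling with generalized estimating equations that include clustering effect of day". Model building follows: "A multivariable model will include sex, gender and variables that have" a univariate p-value below 0.10. No specialist effect, fixed or random, is mentioned.

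SAP 5 says the outcome will be studied "for three fully-qualified ophthalmologists regularly seeing patients with DR". SAP 6.2 states: "Specialist participant characteristics include age, sex, and years as a retina specialist". These are the only physician variables the SAP lists, and it lists them as baseline characteristics.

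**The concern.** A specialist's age, sex and experience are essentially fixed for that person during the trial. However many clinic days are observed, only three values of each trait exist, so the evidence about a trait comes from three people. Clustering on day allows for patients sharing a day. It does not allow for the same three people recurring across days, so each further day counts as new evidence about the trait.

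Two things are at stake. First, an ordinary difference in working speed between three individuals could be reported as an effect of experience, age or sex on productivity, with too small a p-value and too narrow an interval. Second, the 0.10 screen could bring that trait into the adjusted AI versus non-AI model by chance, so the covariate set would depend on a test that does not have its stated error rate.

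**Working it through.** **Inputs from the documents.** Three specialists (SAP 5). Randomisation by clinic day (SAP 5). Total 924 participants, average cluster size 8, day intra-cluster correlation 0.15, control mean 1.34 patients per doctor hour, difference 0.34, alpha 5%, power 80% (SAP 4). Two-sided testing is assumed, because SAP 4 does not state it. The plan gives no figure of its own for physician predictors, so there is none to reproduce.

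**Number of days.** 924 / 8 = 115.5, taken as 116.

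**Step 1: can the traits be separated?** Intercept, age, sex and years make 4 parameters. Three specialists supply at most 3 distinct rows, so the design matrix has rank at most 3 and the full set cannot be estimated. An intercept and any two non-collinear traits already fit the three specialists exactly. This needs no assumption.

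**Step 2: what can one trait support?** With the specialist as the unit, one trait and an intercept leave 3 - 2 = 1 degree of freedom. The two-sided 5% critical t is 12.71 instead of 1.96, and a statistic of 1.96 gives p = 0.30.

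**Step 3: size of the error.** Let τ be the between-specialist SD, σ² the variance of a row that affects the trait contrast, and n the rows per specialist. A specialist's mean has true variance τ² + σ²/n, but the day-clustered analysis sees roughly σ²/n. For a trait with no effect, the test statistic is therefore too large by a factor of about k = √(1 + nτ²/σ²), and the false-positive rate at 5% is about P(|Z| > 1.96/k).

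Assumed: τ = 0.1 patients/h (0.1/1.34 = 7% of the mean) and σ = 0.6.

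- One specialist per day: n = 116/3 = 38.7; nτ²/σ² = 38.7 × 0.01/0.36 = 1.07; k = √2.07 = 1.44; P(|Z| > 1.36) = 17%. At the 0.10 screen, P(|Z| > 1.645/1.44) = 25%.
- Three specialist rows per day: the shared day effect cancels from the contrast and n = 116; 116 × 0.01/0.36 = 3.22; k = √4.22 = 2.05; P(|Z| > 0.95) = 34%. At the screen, 42%.

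Simulation with robust or day-clustered standard errors (example trait values 5, 12 and 20 years; for three rows per day, day SD 0.3 and residual SD 0.6) gave:

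| Between-specialist SD | One specialist per day: 5% test / 10% screen | Three rows per day: 5% test / 10% screen |
|---|---|---|
| 0 | nominal | nominal |
| 0.1 | 17% / 25% | 34% / 42% |
| 0.2 | 38% / 47% | 60% / 66% |
| 0.3 | 53% / 60% | 71% / 76% |

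Repeat runs agreed within about 3 percentage points.

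**Step 4: sensitivity to σ.** The documents give no SD. The value implied by SAP 4, with 115.5/2 = 57.75 days per arm, is 0.34/(1.96 + 0.84) × √(57.75/2) = 0.65. With 0.65, the 17% becomes 16%. The 0.3/0.6 split implies a day correlation of 0.09/0.45 = 0.20. Using the SAP's 0.15 with the same total variance (residual variance 0.85 × 0.45 = 0.3825) gives 33% instead of 34%.

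**Step 5: a second parametrisation.** Here the day correlation was 0.15, the trait patterns differed (years 8/12/25; sex 0/1/0), and patient-level rows were also tried. The 5% test rejected 5-6% of the time with no between-specialist variance, 9-34% when 1% of the variance lay between specialists, and 27-64% at 5%.

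**Step 6: the treatment comparison.** In those same simulations, type I error for AI versus non-AI days was about 5-6% throughout.

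**The case against.** The strongest reply is that the SAP never names specialist age, sex and years as model predictors. They are in a baseline section that comes after SAP 6, so 'above' cannot refer to them. The forced sex and gender terms may be patient variables, since SAP 6.2 also lists age and sex for patients. This stands, and the point is conditional for that reason. It does not clear the plan: physician adjustment is announced, nothing else is offered as a physician variable, and any trait fixed within a specialist meets the same limit.

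The inflation also depends on a between-specialist variance that the documents do not give. This stands too. A reader might infer that the p-values must be far too small; the documents support only that they are too small if the specialists differ, by an amount that depends on how much.

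The rank limit applies only if all three traits enter one model, whereas SAP 6 screens variables one at a time. That is correct; the single-trait tests then carry the problem shown in Step 3.

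The row unit is unclear as well. SAP 2.1 sums over the day and SAP 6 calculates rates for each clinic day, while SAP 3.2 tracks exams for each specialist and SAP 6 speaks of rates per physician. If rows are whole-clinic days pooled over specialists, neither a personal trait nor a specialist factor fits as a row-level covariate. The fix has to cover this case.

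**Conclusion.** The concern holds in conditional form. If the physician predictors are the three traits in SAP 6.2, they cannot be fitted together with an intercept, and day-clustered tests of any one of them reject too often whenever the specialists differ in speed. At a between-specialist SD of 0.1 patients/h the 5% test runs at about 17% (one specialist per day) or 34% (three rows per day), and it is nominal at zero. These figures rest on the assumed between-specialist SD, a day-level SD of about 0.6, 116 days and two-sided testing; only the rank result is free of assumptions.

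A reader might also infer that the trial's main result is compromised. The documents do not support that: AI use is randomised by day, clustering on day is kept, and the error rate of that comparison is not materially affected. No stated outcome concerns physician traits. The harm is confined to the predictor associations and to the choice of covariates for the adjusted estimate. The change is worth making because it costs almost nothing.

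**What to change.** In SAP 6:

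- Replace the reference to predictors 'above' with an explicit list.
- State that specialist age, sex and years of experience are reported descriptively only, are not tested as predictors and do not enter the p < 0.10 screen.
- State the row unit. Analyse specialist-day (or patient) rows with clustering on day, and where the model adjusts for physician, enter specialist as a fixed three-level factor (2 degrees of freedom).
- If rows are whole-clinic days pooled over specialists, do not enter individual traits at all.

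The cost is SAP wording. SAP 3.2 already has exam counts tracked daily for each specialist, and hours tracked daily. The sponsor gives up only p-values for specialist traits, which three people cannot support.
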